## 2. STUDY OBJECTIVES

**Primary outcome:** % time spent in hypoglycaemia (<3.3mmol/L, 60mg/dL)

**Secondary outcome:** % time spent in hypoglycaemia (<2.8mmol/L, 50mg/dL)  
% time spent in hypoglycaemia (<3.9mmol/L, 70mg/dL)  
% time in euglycaemia (3.9-7.8mmol/L, 70-140mg/dL)  
% time spent in target (3.9-10mmol/L, 70-180mg/dL)  
% time spent in hyperglycaemia (>10mmol/L, 180mg/dL)  
Number hypoglycaemic excursions  
Severe hypoglycaemia (requiring third party assistance to treat)  
MAD%  
Glucose variability  
HbA1c  
Sensor usage (compliance)  
Sensor life and % of sensor failure  
% of reported sensor readings compared to total possible readings  
Change in insulin dosage  
Diabetes treatment satisfaction  
CGM usability  
Diabetes quality of life  
Fear of hypoglycaemia  
Healthcare professional qualitative feedback

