### Run-in

Participants will then commence a 2 week run-in phase using the Dexcom G4 sensor with a blinded receiver which stores glucose data but does not make it available to the participant. During the run-in phase participants will wear a Dexcom G4 continuous glucose sensor in the

anterior abdominal wall. The sensor detects glucose in the interstitial fluid and is calibrated to capillary blood glucose values taken a minimum of twice daily. Sensors last seven days and participants will be instructed on how to remove a sensor and implant a new one. This run-in will provide baseline data on glucose control including frequency and severity of hypoglycaemia and information on subject's compliance with frequency of CGM use.

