### **Randomisation**

Participants will then receive standardised CGM education for the Dexcom and Abbott devices from study staff and will be randomised to Libre or the Dexcom G5 system with receiver. All education will be delivered by the research nurse from a predefined curriculum and will be supported by independent written materials. Both the Libre and G5 systems will be used non-adjunctively (without capillary blood glucose verification before making a treatment decision, in accordance with product licences) but participants will be instructed to test their capillary blood glucose if symptoms of hypo- or hyperglycaemia occur, in case of sensor failure or if the sensor glucose is out of the desired range. Participants will use the G5 sensor with the accompanying receiver and will change sensor every seven days (or sooner in the event of sensor failure). Real-time glucose data will be available to participants. Participants will use the Libre sensor with the accompanying receiver and will change the sensor after 14 days (or sooner in the event of sensor failure). Participants will be enabled to use the Libre monitor to assess glucose value and trend as often as they choose.

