### **Follow-Up**

There will be a telephone visit 2 weeks after randomisation with a short, structured interview focusing on the function of the technology and any difficulties with use.

Participants will attend the clinical research facility 4 weeks after randomisation and data will be downloaded from their CGM device and self-monitoring using the Diasend software. At 8 and 16 weeks after randomisation participants will attend the clinical research facility and will have a blood test for HbA1c. They will additionally complete a Gold Score questionnaire, repeat the Quality of Life questionnaires, undergo a semi-structured interview conducted by the research team and data will be downloaded from their CGM device and capillary blood glucose monitor.

After 8 weeks all participants will be offered the opportunity to continue with the Dexcom G5 system for a further 8 week period. The G5 system in the follow-on may be used with the Dexcom receiver or Apple iOS smartphone application and will focus on usability, psychosocial outcomes and qualitative interviews. Participants will change the G5 sensor every seven days (or sooner in the event of sensor failure).

The participants will be provided with a contact number for technical support but insulin titration decisions will be made by the participant.

Quality of life, CGM-related treatment satisfaction and fear of hypoglycaemia data will be collected by mixed quantitative and qualitative methodologies. Validated (Problem Area in Diabetes (PAID), Glucose Monitoring System Satisfaction Survey (GMSS), Hypoglycaemia Fear Survey-II (FHS-II)) and non-validated questionnaires will be used and scripted interviews with participants will be undertaken by the research team to assess the impact of the technology on everyday living with type 1 diabetes. Gold questionnaire will be used to assess impact on hypoglycaemia awareness.

Low glucose alert settings will be standardised at 4.4 mmol/L (80mg/dL) for all participants at the start of the study and can be reduced to 4 mmol/L (70mg/dL) at week 2 depending during

the telephone visit depending on participant preference. High glucose alerts may be personalised.

The study will be completed at the end of the 8 week open label period.

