## **7. STATISTICS AND DATA ANALYSIS**

With 40 participants, we can demonstrate as significant at 80% power a mean difference in time in hypoglycaemia between Libre and G5 of 0.45 standard deviations. Any smaller difference will be distinguished as signifying no significant difference between Libre and CGM. To allow for a 10-15% drop out, 45 participants will be recruited. Randomisation will be stratified by HbA1c quartiles (5-6%, 6.1-7.0%, 7.1-8.0% and 8.1-9%). Randomisation will be done using sealedenvelope.com.

Baseline data will be taken from the first 14 days of monitoring and outcomes will be calculated from the last 30 days in each treatment period.

Analysis will be by intention to treat. The primary outcome will be assessed by two-tailed unpaired t-test. For secondary outcomes parametric data will be compared between the two study arms by two-tailed unpaired t-test for continuous variables. Non-parametric data will be compared using a Kruskal Wallis test.

Data and all appropriate documentation will be stored for a minimum of 10 years after the completion of the study, including the follow-up period.

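### The primary t-test leaves the run-in measurement of the outcome unused; an ANCOVA on it would cost almost nothing and probably add precision

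*Combined protocol and SAP*

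**What the plan says.** Section 2 sets the primary outcome as the percentage of time below 3.3 mmol/L, and the Study Summary says it is measured by a continuous glucose sensor. Section 7 gives the whole of the primary analysis in one sentence: "The primary outcome will be assessed by two-tailed unpaired t-test". No covariate and no change from baseline is mentioned.

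The same quantity can be computed before randomisation. Section 6 (Run-in) says "Participants will then commence a 2 week run-in phase using the Dexcom G4 sensor with a blinded receiver", and gives the purpose: "This run-in will provide baseline data on glucose control including frequency and severity of hypoglycaemia". Participants then "will be randomised to Libre or the Dexcom G5 system with receiver" (Section 6, Randomisation).

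Section 7 fixes two windows. For the first it says "Baseline data will be taken from the first 14 days of monitoring". The second window, used for the endpoint, comes later in the same sentence: "outcomes will be calculated from the last 30 days in each treatment period". Section 6 (Follow-Up) adds that "After 8 weeks all participants will be offered the opportunity to continue with the Dexcom G5 system". The randomised comparison therefore rests on the last 30 days of the first 8 weeks.

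**The concern.** A baseline measurement of the outcome is scheduled for everyone and defined as baseline, but the primary test does not use it. If people with much hypoglycaemia in the run-in tend also to have more at week 8, part of the outcome variance is predictable. The t-test leaves that part in the error term.

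This matters more than usual here for two reasons.

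- The trial plans 40 evaluable participants, and Section 1.2 hypothesises equivalent impact. The width of the confidence interval largely decides what a non-significant result can support.
- Randomisation is stratified by HbA1c only, so nothing balances baseline hypoglycaemia. The baseline difference between arms has standard error √(2/20) = 0.316 SD. A chance imbalance above 0.5 SD (0.5/0.316 = 1.58 standard errors) therefore arises in about 11% of such trials. Adjustment specified in advance deals with it; adjustment decided afterwards invites criticism.

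**Working it through.** **Inputs from the documents.** 40 evaluable participants, 80% power, 0.45 SD, 45 recruited for 10-15% drop-out, two-tailed unpaired t-test (all Section 7).

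**Assumed, because not stated.** Two-sided alpha 0.05; 1:1 allocation, so n = 20 per arm; r from 0 to 0.7; normal data first, then skewed.

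**The plan's own figure.** For two arms of 20, the normal approximation gives a detectable difference of (1.960 + 0.842) × √(2/20) = 0.886 SD. The noncentral t with 38 df gives 0.909 SD. Power at 0.45 SD is 28%. The stated 0.45 SD does not reproduce for this test. That is a separate point, so the comparison below is made at both 0.45 and 0.909 SD.

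**ANCOVA.** The residual SD is SD × √(1 − r²), with 37 df. Chance baseline imbalance inflates the variance by 1 + F/38, where F follows F(1,38). The noncentrality is d / √[(1 − r²)(2/n)(1 + F/38)], and power is averaged over F. The half-width takes the SD as known; for the t-test it is 2.024 × 0.316 = 0.64 SD.

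| Analysis | Power at 0.45 SD | Power at 0.909 SD | Detectable difference, 80% power (SD) | 95% CI half-width (SD) |
|---|---|---|---|---|
| t-test | 28.4% | 80% | 0.909 | 0.64 |
| ANCOVA, r = 0 | 27.8% | 78.9% | 0.922 | 0.65 |
| r = 0.1 | 28.0% | 79.3% | 0.918 | 0.65 |
| r = 0.3 | 30.0% | 82.5% | 0.880 | 0.62 |
| r = 0.5 | 35.2% | 89.0% | 0.799 | 0.56 |
| r = 0.7 | 48.2% | 97.2% | 0.659 | 0.46 |

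**Break-even.** F/38 averages 1/36. Ignoring the lost degree of freedom, ANCOVA breaks even when (1 − r²)(37/36) = 1, so r² = 1/37 and r = 0.164. With the degree of freedom counted, r is about 0.17. The largest loss with 20 per arm is at r = 0: 80% − 78.9%, about 1.1 points.

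**What the gain is worth.** At r = 0.5, (0.909/0.799)² = 1.29, which is what about 29% more participants would buy.

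**With 15% drop-out from 45.** 45 × 0.85 is about 38, or 19 per arm. At 0.909 SD the t-test has 77.8%. ANCOVA has 76.6, 77.0, 80.4, 87.3 and 96.4% at r = 0, 0.1, 0.3, 0.5 and 0.7. The largest loss is 1.2 points.

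**Skewed data.** Log-normal outcome, halved in one arm, r on the log scale, 20 per arm, 200,000 simulated trials per setting:

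| Setting | t-test | ANCOVA at r = 0 / 0.1 / 0.3 / 0.5 / 0.7 |
|---|---|---|
| Log-SD 0.8 | 63-64% | 62.1 / 62.6 / 65.0 / 71.2 / 83.9% |
| Log-SD 1.0 | 40% | 39.0 / 39.3 / 41.1 / 46.2 / 58.9% |
| Log-SD 0.8, 10% zeros in one arm (34% in the halved arm) | 66% | 64.6 / 64.9 / 67.7 / 74.0 / 86.3% |

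At log-SD 0.8 the break-even is a log-scale r of about 0.22 (about 0.17 on the raw scale), and the largest loss is about 1.5 points. At log-SD 1.0 it lies between 0.20 and 0.25. At log-SD 0.8, with or without zeros, type I error is 4.3% for the t-test and 4.3-4.5% for ANCOVA.

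**Missing run-in values.** With 10% missing at random and filled with the overall mean (normal data, 0.909 SD), ANCOVA has 78.9, 81.9, 87.9 and 95.7% at r = 0, 0.3, 0.5 and 0.7, with type I error 5.0%.

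**The case against.** The t-test is valid, no passages conflict, and the whole benefit rests on a correlation that the documents do not give. At r = 0.3 the gain is under 3 points of power. This stands, and it is why the point is an improvement only. The payoff is nevertheless lopsided: at most about 1.5 points lost, against 9 gained at r = 0.5 and 17 at r = 0.7 with normal data.

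The baseline is also not quite the same measurement. It comes from 14 days of blinded Dexcom G4, whereas the outcome comes from 30 days of unblinded data, apparently from each arm's own device. This may lower r, and more so in the Libre arm. Simulated unequal correlations behave like their average: 0.5 in one arm and 0.1 in the other gives 82.5%, as r = 0.3 does; 0.3 and 0 gives 79.6% against 79.8% for the t-test. The range above covers these cases. The covariate precedes randomisation and uses one device in both arms, so it does not bias the comparison.

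Four smaller objections:

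- The t-test might have been meant on change from baseline, though the text does not say so. Its variance factor is then 2(1 − r), against 1 − r² for ANCOVA. Detectable differences are 0.909 against 0.799 SD at r = 0.5, and 0.704 against 0.659 SD at r = 0.7. ANCOVA matches or beats it unless r is close to 1.
- Appendix 1 marks no CGM download at the randomisation visit. That does not override the stated use of the run-in as baseline, but the schedule should be checked.
- The HbA1c stratum could also enter the model. This is optional; the fix works without it.
- With skewed data the choice of scale matters too. At log-SD 0.8 and r = 0 a rank-based ANCOVA has 73.0%, about 9 points above the t-test, and that lead comes from ranking and not from the baseline. It tests a shift in ranks and does not estimate the mean difference.

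**Conclusion.** The concern holds, as an inexpensive improvement to a valid analysis. ANCOVA on the run-in value estimates the same mean difference and gains power unless r is below about 0.17 (normal data) or about 0.22 on the log scale (log-normal, log-SD 0.8). Where the t-test has 80% power, ANCOVA has between 79% and 97% over r = 0 to 0.7.

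The size rests on the assumed r, distribution, alpha and 1:1 allocation. Adjustment does not make 0.45 SD detectable at 80% power with 20 per arm; that would need r of about 0.87. The sample-size statement needs its own correction.

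**What to change.** In Section 7, replace the primary-analysis sentence with the following content:

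- The primary analysis is an ANCOVA of percentage time below 3.3 mmol/L over the last 30 days of the 8-week randomised period, on treatment and run-in percentage time below 3.3 mmol/L. Report the adjusted mean difference with its 95% CI.
- The unpaired t-test is a sensitivity analysis. A rank-based ANCOVA, with midranks for ties, may be pre-specified as a further one for skewness.
- A missing run-in value is replaced by the overall baseline mean, so nobody with outcome data is excluded for lack of a baseline.

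State whether the HbA1c stratum enters the model, and check that Appendix 1 provides for the run-in sensor download. Missing outcomes, with 10-15% drop-out expected, need a separate rule.

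The cost is two or three sentences, one degree of freedom and no new measurements. If r proves low, power falls by up to about 1.2 points with normal data or about 1.5 in the log-normal case.

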## REFERENCE DIAGRAM

# 1. INTRODUCTION

## 1.1 BACKGROUND

Type 1 diabetes (T1DM) is characterised by autoimmune destruction of the pancreatic beta cell, leading to absolute deficiency of insulin. Management of T1DM requires exogenous insulin administration, aiming for glucose concentrations as close to physiological values as possible. Intensive management of T1DM improves glucose control and reduces the risk of microvascular diabetes complications and cardiovascular disease. However, optimal control remains challenging to achieve and intensive insulin treatment increases the risk of severe hypoglycaemia, with lower glucose values also associated with an increased frequency and severity of moderate hypoglycaemia.

Hypoglycaemia is associated with morbidity and even mortality, and places a financial burden on health systems. Severe hypoglycaemia costs £13million per year in direct NHS costs and significantly more in indirect costs to people with diabetes, their families, friends and employers. Hypoglycaemia is one of the most common metabolic complications of the treatment of type 1 diabetes. Mild hypoglycaemia results in a variety of symptoms, including tremor, hunger, and anxiety, and, as glucose concentrations fall lower patients may develop cognitive impairment. Severe hypoglycaemia, defined as hypoglycaemia requiring the assistance of another person to treat, may cause seizures, coma, or death. Between 4 and 10% of deaths in people with type 1 diabetes are attributed to hypoglycaemia and the risk of severe hypoglycaemia increases 6-fold in people with impaired awareness of hypoglycaemia. Avoidance of hypoglycaemia is associated with restoration of hypoglycaemia awareness and this may be enabled by the use of diabetes technology.

Type 1 diabetes directly affects 300,000 people in the United Kingdom. In the UK diabetes consumes more than 10% of the National Health Service budget and in the USA a relatively greater amount is spent on type 1 compared with type 2 diabetes (8.6% of the diabetes budget compared with 5.6% of diabetes prevalence).

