## 3. STUDY DESIGN

Randomised parallel group trial over 18 weeks in 40 adult participants with type 1 diabetes and impaired hypoglycaemia awareness

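### Randomisation is stratified by HbA1c band but the primary t-test leaves the bands out, so the test is conservative to the extent that HbA1c predicts time below 3.3 mmol/L

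*Combined protocol and SAP*

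**What the plan says.** Section 7 (Statistics and Data Analysis) fixes the allocation scheme: "Randomisation will be stratified by HbA1c quartiles (5-6%, 6.1-7.0%, 7.1-8.0% and 8.1-9"%). The bands are called quartiles but are fixed cut-points, so their sizes need not be equal. On method it adds only "Randomisation will be done using sealedenvelope.com", with no block size.

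For the analysis, section 7 says "The primary outcome will be assessed by two-tailed unpaired t-test". Continuous secondary outcomes get the same test if parametric, and a Kruskal-Wallis test otherwise. Neither section 7 nor any other section includes a stratum term, a covariate or a stratified rank test.

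On whether HbA1c matters for the outcome, section 1.1 (Background) describes "lower glucose values also associated with an increased frequency and severity of moderate hypoglycaemia". It also says that real-time CGM reduces hypoglycaemia in people with HbA1c below 7.0%. Neither statement gives a strength of association.

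**The concern.** An unpaired t-test takes its standard error from the total within-arm variance, as if allocation had been simple. Under stratified allocation the arms are held close to balance within each HbA1c band, so differences between bands largely cancel out of the arm comparison. They remain in the t-test's residual variance. If the bands are prognostic, the reported standard error is larger than the real one, any confidence interval built on it is too wide, and the test runs below its nominal level. The precision that stratification was meant to buy is then not used.

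This matters more than usual here because the trial is small. Its hypothesis in section 1.2 is also that the two devices have an equivalent effect, and section 7 reads smaller differences as no significant difference. A test that rejects too rarely leans towards that reading.

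**Working it through.** **Inputs from the protocol.** Two arms (participants "will be randomised to Libre or the Dexcom G5 system with receiver"); 40 analysed (sections 3 and 7); 45 recruited ("To allow for a 10-15% drop out, 45 participants will be recruited"); four HbA1c bands; two-sided unpaired t-test.

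**Assumptions, because the documents give no figure.** Allocation 1:1; alpha 0.05; R², the share of outcome variance explained by HbA1c band, from 0 to 0.3; permuted blocks of 4 or 8 within bands; normal outcome unless stated.

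**Step 1: the plan's own figure.** Section 7 says: "With 40 participants, we can demonstrate as significant at 80% power a mean difference in time in hypoglycaemia between Libre and G5" of 0.45 SD.
- Unpaired formula: n per arm = 2 × (1.96 + 0.8416)² / 0.45² = 77.5, so 78 per arm and 156 in total.
- Power at 20 per arm: Φ(0.45 × √(20/2) − 1.96) = Φ(−0.54) ≈ 30% (28% with the exact t distribution).
- Detectable difference at 20 per arm: (1.96 + 0.8416) × √(2/20) = 0.89 SD (0.91 with exact t).
- One-sample or paired formula: (1.96 + 0.8416)² / 0.45² = 38.8, so 39.

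The stated figure does not reproduce for the planned unpaired test. It fits a paired formula. That is a separate error, but it sets the baseline power for what follows.

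**Step 2: large-sample effect of leaving the bands out.** With arms balanced within bands, the true variance of the difference is multiplied by (1 − R²), while the t-test's estimate is not. So
- SE ratio (reported / true) = 1/√(1 − R²);
- type I error = 2 × [1 − Φ(1.96/√(1 − R²))].

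**Step 3: simulation at this trial's size.** The main run used 40 analysed, blocks of 4, and equal and unequal band shares, with 12,000 null trials per case. Other runs varied the band shares. A less favourable setting had 45 randomised, 5 random dropouts and blocks of 8.

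| R² | Large-sample SE ratio | Large-sample type I | Type I, 40 analysed, blocks of 4 | Type I, 45 randomised, 5 lost, blocks of 8 |
|---|---|---|---|---|
| 0 | 1.00 | 5.0% | about 4.9% | about 5% |
| 0.1 | 1.05 | 3.9% | 4.0–4.4% | 4.2–4.4% |
| 0.2 | 1.12 | 2.8% | 2.8–3.2% | 3.6–3.7% |
| 0.3 | 1.20 | 1.9% | 2.2–2.4% | about 3.2% |

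Mean reported SE over true SD of the difference in the main run (equal; unequal bands):
- R² 0.1: 0.3148/0.3032 = 1.04; 0.3152/0.3020 = 1.04.
- R² 0.2: 0.3153/0.2868 = 1.10; 0.3151/0.2836 = 1.11.
- R² 0.3: 0.3157/0.2693 = 1.17; 0.3154/0.2749 = 1.15.

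With dropout and blocks of 8 the excess shrinks to about 3%, 5–7% and as little as 9%. In the main run the stratum-adjusted model held its type I error at 4.7–5.3%. With a lognormal outcome (R² set on the log scale) the t-test's type I error was 4.6%, 3.3% and 2.2% at R² of 0, 0.1 and 0.3, the same direction.

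**Step 4: power, unadjusted against stratum-adjusted.**

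| R² | True difference 0.45 SD | True difference 0.90 SD |
|---|---|---|
| 0 | 28–29% vs 28–29% | 80% vs 79% |
| 0.1 | 26–28% vs 30–31% | 81% vs 83% |
| 0.2 | 25–26% vs 32–34% | 82% vs 87% |

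**The case against.** The strongest reply is that the whole effect is conditional. A reader might infer that the standard error is simply wrong and the true type I error is below 5%. The documents do not support that. The first Background statement concerns lower glucose under intensive treatment generally. It does not say that screening HbA1c predicts sensor time below 3.3 mmol/L over the last 30 days of treatment, in people all selected for a recent severe event or a Gold score of at least 4. An R² of 0.2 or 0.3 has no source in the protocol. At R² = 0 there is no distortion, and at 0.05 the type I error is 4.5–4.7%. This objection stands, and the point is worded conditionally because of it.

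Three other stronger readings also fail.
- That the t-test is invalid: it is not. The error is conservative and false positives are not inflated.
- That an over-wide interval decides the equivalence question: section 7 specifies no confidence interval and no equivalence margin. Treating non-significance as equivalence is a different defect.
- That adjustment rescues the trial: at the protocol's own 0.45 SD, power remains near one third even at R² = 0.2.

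Adjusting for the run-in sensor value would probably absorb part of what HbA1c explains, so the two gains overlap and should not be added.

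What the reply does not remove is the mismatch. The design uses the bands, the analysis does not, and aligning them costs almost nothing.

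**Conclusion.** The point holds in conditional form. The primary analysis omits the factor by which allocation is stratified. If HbA1c band explains 10%, 20% or 30% of the outcome variance, the t-test's standard error is about 3–4%, 5–11% or 9–17% too large. Its type I error is then about 4%, 3–3.7% or 2.2–3.2% in place of 5%. The spread reflects block size, dropout and band shares. If HbA1c is not prognostic, nothing is lost by the present plan.

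The results rest on an assumed R², two-sided alpha of 0.05, 1:1 allocation and permuted blocks within bands, none of which the documents state. The omission itself is certain; the size of its effect is not. This is a cheap improvement in precision. It is not a threat to validity and not a remedy for the sample-size statement.

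**What to change.** In section 7, replace the sentence naming the primary test with:

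*The primary outcome will be compared by a linear model with terms for arm and HbA1c randomisation stratum; the adjusted difference and its 95% CI will be reported.*

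Before any outcome data are seen, also state:
- one rule for sparse bands, for example merging any band with fewer than a stated number of participants into its neighbour;
- how a participant with HbA1c above 9% is classified, since the bands stop at 9% and sections 4.2 and 4.3 set no HbA1c limit.

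Alternatively, prespecify screening HbA1c as a single linear term, which needs neither rule. Choose one option now, so that the model is not selected after the results are known.

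Use the same term for the continuous secondary outcomes, and the van Elteren (stratified rank) test wherever a rank test is used.

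Cost: a few sentences and no new data, since HbA1c is already measured at screening (section 6 and Appendix 1). The model uses up to 3 degrees of freedom and loses about one point of power or less if HbA1c turns out not to be prognostic.
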